### **7.9.6 Assessment of Adverse Events**

#### **7.9.6.1 Assessment of Severity**

Severity of AEs will be graded according to the following definitions:

Mild: AE that was easily tolerated

Moderate: AE sufficiently discomforting to interfere with daily activity

Severe: AE that prevented normal daily activities

#### **7.9.6.2 Assessment of Causality**

A medically qualified investigator must assess the relationship of any AE (including SAEs) to the use of the study device as unlikely related, possibly related, or probably related based on available information, using the following guidelines:

Unlikely related: no temporal association, or the cause of the event has been identified, or the study device cannot be implicated based on available information

Possibly related: temporal association but other etiologies are likely to be the cause; however, involvement of the study device cannot be excluded based on available information

Probably related: temporal association, other etiologies are possible, but unlikely based on available information

#### **7.9.6.3 Reference Safety Information for Assessing Expectedness of Adverse Events**

The reference safety information for assessing the expectedness of an AE for the study device in this study is the [PN40082 Instructions for Use](#) and the [Restylane® Silk Instructions for Use](#).

### **7.9.7 Reporting Safety Observations**

Any SAE, whether deemed device-related or not, must be reported to the Sponsor or designee by telephone, email or fax as soon as possible after the investigator or coordinator has become aware of its

occurrence. The investigator/coordinator must complete a Serious Adverse Event (SAE) Form and email or fax it to the Sponsor or designee along with the subject's Adverse Events Log and Concomitant Medications Log within 24 hours of notification of the event. The Sponsor will notify the FDA of device-related SAEs.

Designee and Sponsor contact details:

[REDACTED]	[REDACTED]	[REDACTED]
[REDACTED]	[REDACTED]	Prollenium Medical Technologies, Inc. [REDACTED]

The investigator must be prepared to supply the medical monitor with the following information:

1. Investigator name and site number
2. Protocol number
3. Subject ID (screening/randomization) number
4. Subject initials and date of birth
5. Subject demographics
6. Clinical event
  - a. description
  - b. date of onset
  - c. severity
  - d. treatment (including hospitalization)
  - e. relationship to study device
  - f. action taken regarding study device
  - g. if the AE was fatal or life-threatening:
    - i. cause of death (whether or not the death was related to study device)
    - ii. autopsy findings (if available)

The Sponsor must submit a written summary of the clinical course of any life-threatening SAE and related subject information to the FDA within 7 days. Serious and unexpected AEs that are not life-threatening must be reported to the FDA within 15 calendar days. Any serious and unexpected AE

(including all deaths) must also be reported to the Institutional Review Board (IRB) by the investigator according to IRB reporting requirements and documentation of this report sent to the Sponsor or designee.

The investigator must provide a follow-up written report within 5 calendar days of reporting the event to the medical monitor. The written report must contain a full description of the event and any sequelae. Subjects who have had an SAE must be followed clinically until all parameters (including laboratory) have either returned to normal or are stabilized.

#### **7.9.8 Diary Assessments**

Diaries will be reviewed by the Treating Investigator and/or unblinded staff each time they are returned by a subject. Entries will be reviewed for completeness and medical accuracy. Any diary events listed by the subject as persisting beyond the final recording day of the diary will be evaluated by the Treating Investigator at the next visit and may be recorded as an AE at the discretion of the investigator.

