#### **7.4.4 Blinding of Study Device**

Injections of the study device are performed by the unblinded Treating Investigator. The blinded Evaluating Investigator is not allowed to retrieve study supplies or to be present during opening of the study supplies or during the injections. The Treating Investigator is not to have any discussion with the Evaluating Investigator or subjects regarding the treatments.

Subjects are blinded to treatment assignment. Subjects are physically masked (blindfolded) just prior to and during all injection procedures to prevent observation of the syringes containing study device.

Subjects, investigators, the Sponsor's staff conducting the study, and members of the administrative team will not have access to individual subjects' treatment assignments. In the event of an emergency that requires breaking of the study blind, the randomization code will be maintained by each investigator that can be opened to reveal the study device.

See Section 7.9.10.2 for a description of the method of unblinding a subject during the study if such action is warranted.

At Visit 5, subjects and blinded evaluating investigators will be asked which treatment they thought was administered as a way of evaluating the blinding.

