#### **7.6.1 Study Roles**

Each site will designate at least one Treating Investigator and at least one blinded Evaluating Investigator. In addition, one or more members of the study site staff may be designated as unblinded for the purposes of assisting in the management of study device use. Any study staff designated as unblinded should have no direct contact with subjects and may not perform any subject evaluations, assessments or measurements (including vital signs, questionnaires, etc.). Designation of unblinded study staff will be recorded in the Delegation of Authorities Log form.

The Treating Investigator will be responsible for conducting the injections, ensuring that the correct randomized study device is administered in accordance with the protocol and other study instructions. The Treating Investigator will assess subjects and determine the need for touch-up injections. Any AEs brought to the attention of the Treating Investigator will be forwarded to the blinded Evaluating Investigator for final adjudication and documentation.

The blinded Evaluating Investigator will be responsible for assigning grades for the various parameters (LFGS, POL, iGAI, lip function, lip sensation etc.). The blinded Evaluating Investigator will be responsible for recording AEs and determining their severity and relationship to the study device or the injection procedure.

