## **7.9 Assessment of Safety**

### **7.9.1 Safety Analysis**

Safety of the study devices will be compared by evaluating the nature, severity, and frequency of treatment-emergent adverse events (TEAEs). All AEs that occur during the study will be recorded whether or not they are considered to be related to treatment. A description of the AE will be recorded with the date of onset, date of resolution, severity of the AE, relationship to the study device, action taken, and the outcome.

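### Protocol 7.9.8 makes AE recording optional for diary events that outlast the diary, after evaluation by the unblinded Treating Investigator, and so contradicts Protocol 7.6.1 and 7.9.1 and SAP 5.6.1

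*Protocol*

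**What the plan says.** Protocol 7.9.8 (Diary Assessments) sets the route for diary data: "Diaries will be reviewed by the Treating Investigator and/or unblinded staff each time they are returned by a subject". The review covers whether entries are complete and medically accurate. For longer-lasting events the section adds: "Any diary events listed by the subject as persisting beyond the final recording day of the diary will be evaluated by the Treating Investigator". Such an event then "may be recorded as an AE at the discretion of the investigator". The section does not say whether that is the Treating or the Evaluating Investigator.

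The Treating Investigator knows the arm. Protocol 7.4.4 states: "Injections of the study device are performed by the unblinded Treating Investigator".

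Other sections describe a different route:

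- Protocol 7.6.1 on recording: "The blinded Evaluating Investigator will be responsible for recording AEs and determining their severity", and also their relationship to the device or procedure.
- Protocol 7.6.1 on events that reach the unblinded side: "Any AEs brought to the attention of the Treating Investigator will be forwarded to the blinded Evaluating Investigator for final adjudication and documentation".
- Protocol 7.6.24: the diary card is given to subjects so that they can note AEs in the two weeks after the initial and any touch-up treatment.
- Protocol 7.9.1: "All AEs that occur during the study will be recorded whether or not they are considered to be related to treatment". SAP 5.6.1 repeats that all AEs are recorded and coded.
- SAP shells: Table 14.3.2.1 has separate columns for TEAEs reported by subjects and by investigators. The example rows in Listings 16.2.7.1.1 and 16.2.7.1.2 give the subject diary as the source of the AE.

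**The concern.** The blinding scheme depends on keeping outcome judgements with someone who does not know the arm. Section 7.6.1 does that for AEs. Section 7.9.8 inserts an earlier step, carried out by people who do know the arm, and at the end of that step recording is optional.

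The clause falls on the events that last longest, which are of particular interest in a filler comparison. Protocol 7.9.1 says the devices will be compared on the nature, severity and frequency of TEAEs. The SAP also summarises duration in bands of under 7, 7 to 30 and over 30 days (Table 14.3.2.8) and lists events lasting over 30 days (Listing 16.2.7.4). Those duration outputs are titled for vascular-injection and visual events. However, the row label in related Table 14.3.2.1 refers to injection-site events, and the example in Listing 16.2.7.1.1 is an injection-site swelling, so persisting local reactions appear to belong there. If persisting events are dropped more readily in one arm, both the frequency and the duration comparison are distorted, and nothing in the tables would show it.

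**Working it through.** The plan states no figure on this point, so there is none to reproduce. The check is a comparison of sections, followed by an illustration of size.

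**Step 1: follow one event through the text.** Take lip swelling that a subject marks as still present on the last diary day.

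| Section | What happens to the event |
|---|---|
| Protocol 7.6.24 | It is on the card because the card collects AEs |
| Protocol 7.9.3.1 | Injection-site swelling is named among the expected adverse events, so it is an AE |
| Protocol 7.9.1, SAP 5.6.1 | It is recorded, with no discretion |
| Protocol 7.6.1 | The blinded Evaluating Investigator records and grades it |
| Protocol 7.9.8 | The unblinded Treating Investigator evaluates it, and recording is optional |

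A site cannot apply the discretion in the last row and also comply with the rows above it.

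**Step 2: does the forwarding rule in 7.6.1 close the gap?** Forwarding applies to AEs. Section 7.9.8 lets someone decide beforehand whether a persisting diary event is to count as one. An event judged not to be an AE at that step need not be forwarded, so the blinded adjudication never sees it.

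**Step 3: size, as an illustration only.** The documents give no rate of persisting diary events for this trial.

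Inputs:

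- Planned size: 158 randomized, 79 per arm (Protocol 8.5).
- Proxy for persistence: in the comparator label's diary table (study MA-1700-04, first treatment), 15 of the 213 subjects with swelling had it on all 14 diary days. 15/213 = 7.0%. With all 218 treated subjects as the denominator it is 15/218 = 6.9%. I use p = 0.07 in both arms. That this rate applies here is an assumption.

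Subjects under the clause, per arm: 79 × 0.07 = 5.5, or about 5 to 6.

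If a fraction f of these is left unrecorded in one arm only, the false difference is p × f:

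| f | Subjects omitted (5.5 × f) | False difference |
|---|---|---|
| 0.25 | 1.4 | 0.07 × 0.25 = 1.75 points |
| 0.50 | 2.8 | 0.07 × 0.50 = 3.5 points |
| 1.00 | 5.5 | 0.07 × 1.00 = 7.0 points |

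For scale, the 95% half-width for a difference between two arms of 79, both at 7%, is 1.96 × √(2 × 0.07 × 0.93 / 79) = 1.96 × 0.0406 = 0.080, or about 8 points. The shift would lie within sampling error, but unlike sampling error it is avoidable.

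**The case against.** The case on the other side has several good parts.

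- **The clause is narrow.** It reaches only events that outlast the diary. Other entries are reviewed by unblinded people, but 7.9.8 gives no stated power to discard them. This stands, and the point is limited accordingly.
- **The discretion may not be unblinded.** The clause says only the investigator, and read with 7.6.1 that could be the blinded evaluator. This stands as an ambiguity. It does not remove the problem, because the evaluation before the decision is assigned to the Treating Investigator by name, and recording is optional whoever decides.
- **There are other routes into the record.** AEs are asked about at the Day 3 and Day 14 calls and at Visits 2 and 3 (Protocol 7.7.2, 7.7.3, 7.7.5), and subjects are questioned throughout (7.9.5). A persisting event may be caught there. This reduces the risk but does not remove it. The diary period ends about two weeks after treatment and the next visit is Day 28, so an event that resolves in between may be documented only on the card. Under 7.9.5 specific AEs are not to be prompted.
- **The bar on assessments is aimed elsewhere.** The rule in 7.6.1 that unblinded personnel "may not perform any subject evaluations, assessments or measurements" concerns site staff designated to help manage the device. The Treating Investigator is described separately and does assess subjects for touch-up. Whether checking a returned card is an assessment is arguable. I therefore do not rest the contradiction on that sentence.
- **Safety is descriptive.** There is no safety margin and no between-arm safety test (Protocol 8.4, SAP 5.6.1). This stands and limits the consequence.

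A reader might go further. In the comparator label, swelling was noted by 98% of subjects in diaries while lip swelling was a TEAE in 43%, and a reader could infer that unblinded discretion can move TEAE rates by tens of points. The documents do not support that. The diary in that study solicited six named symptoms, whereas the one here collects AEs that subjects experience. The gap is between two data sources pooled over treated subjects, and not between arms. And the clause here reaches only persisting events.

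**Conclusion.** Wrong as written, as an internal contradiction; confidence is moderate. Protocol 7.9.8 cannot be reconciled with 7.6.1, 7.6.24, 7.9.1 and SAP 5.6.1 on whether a persisting diary event is recorded as an AE, and it leaves open who decides. It allows longer-lasting events to be screened out with knowledge of the arm before they reach the blinded evaluator.

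The consequence is possible bias in the descriptive TEAE frequency and duration summaries. Its direction cannot be predicted from the documents. The illustrated shift of about 2 to 7 points rests on three assumptions: the 7% rate carries over from the comparator label, 25% to 100% of those events go unrecorded, and the omission occurs in one arm only. Equal omission in both arms would lower both rates and, with equal true rates as assumed here, create no difference. Nothing shows that such omission will happen; the text permits it.

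It would be too strong to conclude that the unblinded investigator decides the fate of all diary events, or that the efficacy result is at risk. The primary non-inferiority analysis uses the blinded LFGS assessment and does not depend on AE recording.

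**What to change.** Amend Protocol 7.9.8 in two places:

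1. Have all returned diary entries, including events that continue past the last diary day, passed to the blinded Evaluating Investigator, who reviews them and records them as AEs with severity and start and stop dates. The Treating Investigator may still see the diary, but the recording decision does not sit there.
2. Delete the clause that makes recording discretionary.

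Section 7.9.8 then agrees with 7.6.1, 7.9.1 and SAP 5.6.1. The SAP shells need no change, since they already provide for diary-sourced AEs.

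If diaries have already been processed under the present text, compare the cards with the AE records and report, by arm, how many persisting entries were not recorded.

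The cost is a wording change and some additional AE lines to enter. Each site already has a blinded Evaluating Investigator, so no new staff are needed, and no treatment or clinical rule changes.

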#### **7.9.9 Criteria for Early Termination of the Study**

The trial may be terminated because of safety concerns. Where termination is deemed appropriate, there will be timely communication with the FDA in accordance with the regulation (21 CFR 812.150 (devices)). The sponsor, Prolenium Medical Technologies, will initiate discussion as soon as possible about the appropriate course of action for the trial in question and for the investigational product. There will be immediate follow up by the company to investigate any potential safety concern.

In the event of a vascular embolic event leading to skin necrosis, vision loss, or stroke, enrollment and treatment at the investigational site will be suspended and a root cause investigation will be conducted to determine the cause of the embolic event and whether the outcome was anticipated (the investigator did not properly follow the treatment SOP) or unanticipated (the investigator did properly follow the treatment SOP). If the latter situation is observed, the entire study will be immediately suspended and no patients will be enrolled until the event can be properly characterized and an appropriate treatment strategy to avoid this unanticipated event can be devised.

#### **7.9.10 Withdrawal, Treatment Interruption, and Unblinding of Blinded Treatment Due to Safety Observations**

##### **7.9.10.1 Withdrawal**

See Section 7.3.3 for the criteria for withdrawing a subject. If a subject is withdrawn from the study, the activities specified for Visit 5/Month 6 on the schedule of study activities (Section 2) should be completed if possible.

##### **7.9.10.2 Unblinding Treatment for a Subject During the Study**

Unblinding by the investigator should occur only in the event of an AE or SAE for which it is necessary to know the study treatment to determine an appropriate course of therapy for the subject. In the event of an emergency that requires breaking of the study blind, the Investigator can unblind the subject without prior contact with the Medical Monitor although the Investigator will immediately notify the Medical Monitor accompanied by a written explanation of the reason why the blind was broken. In the event of an emergency that requires breaking of the study blind, the randomization code will be maintained by each unblinded Treating Investigator that can be opened to reveal the study device to the applicable staff. In the event the unblinded Treating Investigator is not available, the site should designate another unblinded staff member not involved in the study conduct to access the randomization code for that

subject. Note this can be done WITHOUT informing the blinded Evaluating Investigator and thus maintaining the study blind. If unblinding occurs, the subject must be withdrawn from the study.

## 8 STATISTICAL METHODS

Prior to the database lock, a detailed, finalized Statistical Analysis Plan will be completed and placed on file. The Statistical Analysis Plan will contain a more comprehensive explanation than that provided here of the methodology used in the statistical analyses, as well as the rules and data handling conventions used to perform the analyses and the procedure used to account for missing data.

### 8.1 Analysis Populations

Intent-to-treat (ITT) (safety) population: All randomized subjects who received study device

Modified intent-to-treat (mITT): All randomized subjects who met the inclusion/exclusion criteria, were randomized, and received study device

Per-protocol (PP): All randomized subjects who met all inclusion/exclusion criteria; received study device, completed Visit 5 within the specified window; had LFGS score by the Blinded Evaluating Investigator at Visit 3/Month 2 within the specified visit window, and had no significant protocol violations that would affect the treatment evaluation

Efficacy analyses will be performed on the mITT and PP populations, with PP as the primary population and mITT supportive.

Safety analyses will be performed on the ITT population.

### 8.2 Efficacy Analysis

The primary efficacy endpoint is change from baseline to Month 2 in overall lip fullness based on the Blinded Evaluating Investigator assessment using the LFGS. A 95% confidence interval (CI) will be constructed for the difference between PN40082 and Restylane Silk (i.e. PN40082 minus Restylane Silk) with respect to the primary endpoint. If the lower limit of this 95% CI is above a pre-specified NI limit - 0.50, PN40082 will be claimed non-inferior to Restylane Silk.

The primary endpoint will also be analyzed for the following two subsets of subjects: (1) subjects that have injection on one lip only, and (2) subjects that have injections on both lips.

Secondary analysis include

- percent of subjects with treatment success (responder: overall LFGS based on the Blinded Evaluating Investigator Assessment) at Visit 3/Month 2 where responder is defined as a subject with at least a 1-grade increase from baseline on the LFGS post augmentation,
- percent of responders overall on the POL severity scale at Visit 4/Month 3 (defined as a subject demonstrating  $\geq 1$ -point improvement, i.e., decrease in severity, from baseline),
- change from baseline to Visit 4/Month 3 in overall LFGS based on the Blinded Evaluating Investigator Assessment
- change from baseline to Visit 5/Month 6 in overall LFGS based on the Blinded Evaluating Investigator Assessment.

For this non-inferiority study, the null hypothesis to be tested for all the secondary endpoints is that there is no difference between the two products, and all statistical comparisons for these endpoints will be considered descriptive (non-inferential). These secondary variables will be summarized with descriptive statistics for

each treatment arm and a 95% CI for the difference between treatments. For the proportion variables, the 95% CI for treatment difference will be calculated using the Wald's method, with subjects pooled from all study sites. For the change variables, the 95% CI for treatment difference will be derived using ANCOVA with factors of treatment and site, and the corresponding baseline value for the endpoint as covariate.

Other efficacy analysis include

- pGAI, iGAI, and Swelling Assessment at each scheduled visit,
- percent of subjects with treatment success (responder: upper lips, lower lips LFGS) at Visit 3/Month 2 where responder is defined as a subject with at least a 1-grade increase from baseline on the LFGS post augmentation,
- percent of responders (upper lips, lower lips) on the POL severity scale at Visit 4/Month 3 (defined as a subject demonstrating  $\geq 1$ -point improvement, i.e., decrease in severity, from baseline),
- satisfaction with lips VAS at each scheduled visit,
- change from baseline to Visit 4/Month 3 and Visit 5/Month 6 in upper lips, lower lips LFGS.

All other efficacy endpoints will be summarized by treatment arm using descriptive statistics.

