#### 7.4.2 Randomization

Subjects who satisfy all of the eligibility criteria will be randomized in a 1:1 ratio to treatment with PN40082 or Restylane Silk. Randomization will be performed according to a computer-generated randomization scheme that will be generated and maintained by an independent third party. A sealed copy of the randomization scheme should be retained at each site and should be available to regulatory authorities at the time of site inspection to allow for verification of the treatment identity for each subject.

A unique subject number will be assigned to each subject. Each site will receive the randomization scheme. Each eligible subject will be assigned a unique randomization code number in ascending order.

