10. The lips should be augmented to achieve the maximum desirable appearance for both the treating investigator and the subject. Subjects should be provided a small hand mirror to observe the results and further injections conducted until maximum benefit has been obtained. Care should be taken to ensure that the lips are symmetric from right to left and that the upper and lower lips have relative proportionality.
11. The perioral area should be corrected AFTER the upper and lower lips have been corrected. Some correction of perioral rhytids may occur with lip augmentation, thus it is best to address any remaining perioral correction needs after the lip injections have been completed.
12. If the treated area is swollen directly after the injection, an ice pack can be applied on the site for a short period if the investigator deems it appropriate. Ice should be used with caution if the area is still numb from anesthetic to avoid thermal injury.
13. Subjects should be encouraged to avoid a recumbent position for several hours after injections to reduce swelling. The use of ice, cold packs or other therapies to reduce swelling should only be performed at instruction of the investigator. The subject should be instructed to contact the site if substantial swelling occurs.

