### **7.5 Study Schedule**

The visit-by-visit schedule of study activities is provided in Section 2. The timing of each visit is relative to Day 1, which is defined as the day the subject is randomized and first treated.

All visits should be performed within the windows specified on the schedule of study activities. Every attempt should be made to have each subject attend each visit as scheduled. If a subject is unable to attend a visit within the specified window the visit should be scheduled as closely as possible to the applicable window.

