5.5.1 Primary Efficacy Analysis

The primary efficacy endpoint is change from baseline to Visit 3/Month 2 in overall LFGS. The null hypothesis to be tested is that the Test device is inferior to the Control device. The results for PP are considered as definitive and those for mITT as supportive.

Summary statistics (mean, SD, minimum, median, maximum) and 95% confidence interval (CI) for mean will be presented for the changes scores for each treatment.

Due to the fact that the change scores would only contain 5 possible values (0, 1, 2, 3, and 4), the normal distribution assumption is hardly attainable, and therefore, the nonparametric Hodges-Lehmann (HL) estimators will be employed to test the study hypothesis. The 95% confidence limits for the median differences between the two treatment groups (PN40082 minus Restylane Silk) will be derived using PROC NPARIWAY with the option for the HL estimators. If the lower limit is on or above -1.0, the null hypothesis will be rejected to support the claim that PN40082 is non-inferior to Restylane Silk.

For the mITT analysis, the above analysis will be carried out for each copy of the MI data sets. Then PROC MIANALYZE will be performed to account for the between and within variation in the multiply imputed data sets.

To assist an assessment for the consistency of the treatment effect among sites, summary of the primary endpoint will be presented by site for the primary population (i.e., the PP subjects).

The primary endpoint will also be analyzed for the following two subsets of the PP subjects: (1) subjects that have injection on one lip only, and (2) subjects that have injections on both lips.

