Table 14.2.1.3 – Supportive Analysis of Primary Efficacy by Study Site for Per-Protocol Population: Change from Baseline to Visit 3/Month 2 in Overall Lip Fullness Grading Scale (LFGS)

Site Number	Statistics	PN40082	Restylane Silk
1	N	0	0
	Mean ± SD	0.0 ± 0.00	0.0 ± 0.00
	95% CI of Mean	(0.00, 0.00)	(0.00, 0.00)
	Median	0.0	0.0
	Min, Max	0, 0	0, 0
	Median Differences and 95% Confidence Limits for PN40082 minus Restylane Silk	0.0 (0.0, 0.0) ¹	
2			
...			
6	N	0	0
	Mean ± SD	0.0 ± 0.00	0.0 ± 0.00
	95% CI of Mean	(0.00, 0.00)	(0.00, 0.00)
	Median	0.0	0.0
	Min, Max	0, 0	0, 0
	Median Differences and 95% Confidence Limits for PN40082 minus Restylane Silk	0.0 (0.0, 0.0) ¹	

LFGS: 0=Very Thin Lips, 1=Thin Lips, 2=Moderately Thick Lips, 3=Thick Lips, 4=Full Lips.

For the mITT analysis, missing overall LFGS scores will be replaced using the multiple imputation (MI) approach.

¹Median differences and 95% confidence limits are derived using Hodges-Lehmann estimators from PROC NPARIWAY.

Source: Listing 16.2.6.2.3

O:\Studies\Prolenium\SYM 2018-02\Biometrics\Programs\Tables\cxxx.sas ran on Month Day, Year at hh:mm on data from Month, Day, Year.

Table 14.2.1.4 –Supportive Analysis of Primary Efficacy Endpoint by Subject Subset for Per-Protocol Population: Change from Baseline to Visit 3/Month 2 in Overall Lip Fullness Grading Scale (LFGS) for Who Had Injection on One Lip Only Versus Who Had Injections on Both Lips

Subset	Statistics	PN40082	Restylane Silk
Subjects Who Had Injection on One Lip Only	N	0	0
	Mean ± SD	0.0 ± 0.00	0.0 ± 0.00
	95% CI of Mean	(0.00, 0.00)	(0.00, 0.00)
	Median	0.0	0.0
	Min, Max	0, 0	0, 0
	Median Differences and 95% Confidence Limits for PN40082 minus Restylane Silk	0.0 (0.0, 0.0) ¹	
Subjects Who Had Injections on Both Lips	N	0	0
	Mean ± SD	0.0 ± 0.00	0.0 ± 0.00
	95% CI of Mean	(0.00, 0.00)	(0.00, 0.00)
	Median	0.0	0.0
	Min, Max	0, 0	0, 0
	Median Differences and 95% Confidence Limits for PN40082 minus Restylane Silk	0.0 (0.0, 0.0) ¹	

LFGS: 0=Very Thin Lips, 1=Thin Lips, 2=Moderately Thick Lips, 3=Thick Lips, 4=Full Lips.

For the mITT analysis, missing overall LFGS scores will be replaced using the multiple imputation (MI) approach.

¹Median differences and 95% confidence limits are derived using Hodges-Lehmann estimators from PROC NPARIWAY.

Source: Listing 16.2.6.2.3

O:\Studies\Prolenium\SYM 2018-02\Biometrics\Programs\Tables\xxx.sas ran on Month Day, Year at hh:mm on data from Month, Day, Year.

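### The one-lip and both-lips subsets of the primary endpoint are defined by lips actually injected, which is settled after randomization, so the device comparison within each subset is not protected by randomization

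*Protocol*

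**What the plan says.** **Definition.** Protocol 8.2 splits the Month 2 change in overall LFGS by injection received: "The primary endpoint will also be analyzed for the following two subsets of subjects: (1) subjects that have injection on one lip only", against subjects injected in both. SAP 5.5.1 repeats the split within the per-protocol population: "The primary endpoint will also be analyzed for the following two subsets of the PP subjects". The shell of Table 14.2.1.4 puts it in the past tense ("Subjects Who Had Injection on One Lip Only"), gives a Hodges-Lehmann difference between devices with 95% limits for each subset, and is titled as a supportive analysis.

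**Order of events.** Protocol 7.4.2: "Subjects who satisfy all of the eligibility criteria will be randomized in a 1:1 ratio to treatment with PN40082 or Restylane Silk". No stratification factor is named. Section 7.5 speaks of "Day 1, which is defined as the day the subject is randomized and first treated", and the Visit 1 list in 7.7.1 puts randomization ahead of treatment.

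**Who acts, and on what basis.** Section 7.4.4: "Injections of the study device are performed by the unblinded Treating Investigator". Under Injection Techniques, item 10: "The lips should be augmented to achieve the maximum desirable appearance for both the treating investigator and the subject". The subject is given a mirror, with "further injections conducted until maximum benefit has been obtained", and upper and lower lips are to be kept in proportion. A touch-up at Visit 2 (Day 28) is decided by the Treating Investigator in consultation with the subject (7.6.12), before the Day 56 endpoint.

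**Baseline information on lips.** The only related item is inclusion criterion 3. It mentions a wish for treatment of one or both lips, and only for Fitzpatrick IV to VI subjects with thick or full lips.

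**The concern.** A subset comparison keeps the benefit of randomization when membership is fixed by something known before assignment. Here membership is an event that follows assignment. If one device gives less fullness or poorer proportion in the first lip, some of its subjects may have the second lip treated where the other device would have left them as one-lip subjects. The one-lip group in one arm would then hold a different kind of subject from the one-lip group in the other, and so would the both-lips groups. Part of any difference in Table 14.2.1.4 would reflect who was sorted into the subset rather than how the device performed.

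The number of lips treated is also likely to bear on the score, because overall LFGS grades the two lips together (Protocol 7.6.9). What is at stake is how one supportive table is read: a reader could take consistent, or inconsistent, subset results as evidence about the device.

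**Working it through.** **1. Is membership fixed before or after assignment?**
- Subset wording: lips injected (Protocol 8.2, SAP 5.5.1, Table 14.2.1.4).
- Sequence: eligibility, randomization, injection (7.4.2, 7.7.1), then a possible touch-up at Day 28 and the endpoint at Day 56.
- Neither document records intended lips for all subjects before randomization, stratifies on them, or adjusts for them.

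Membership is therefore fixed after assignment.

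**2. The plan's own figure.** It is checked here only because the illustrations borrow its SD and its number per arm. Inputs from Protocol 8.5: SD 0.85, margin 0.50, true difference 0, 90% power; one-sided 0.025 from the 95% CI.
- n per arm = 2 × [0.85 × (1.960 + 1.282) / 0.50]² = 60.7, so 61 by the normal formula, or 62 with the t distribution. Power at the stated 63 per arm is 90.6%.
- 126 / 0.80 = 157.5, so 158 randomized.

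The stated figures are reproduced.

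**3. How large could the selection effect be?** The documents give no one-lip share, so every share below is an assumption. Suppose the devices are truly equal, SD is 0.85, and a latent tendency L has correlation ρ with the change score. A subject is treated in one lip when L falls below the normal quantile z(p), where p is the one-lip share in that arm. With φ the normal density:
- mean change in the one-lip group, relative to the arm mean = −0.85 ρ φ(z(p)) / p
- mean change in the both-lips group, relative to the arm mean = +0.85 ρ φ(z(p)) / (1 − p)

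For p = 0.10, 0.15, 0.25 and 0.30, φ/p is 1.755, 1.554, 1.271 and 1.159, and φ/(1 − p) is 0.195, 0.274, 0.424 and 0.497. Example: one-lip subset, 15% v 25%, ρ = 0.3: −0.85 × 0.3 × (1.554 − 1.271) = −0.07.

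| One-lip share, PN40082 v Restylane Silk | ρ | False difference, one lip | False difference, both lips |
|---|---|---|---|
| 20% v 20% | any | 0 | 0 |
| 15% v 25% | 0.3 | −0.07 | −0.04 |
| 15% v 25% | 0.5 | −0.12 | −0.06 |
| 10% v 30% | 0.3 | −0.15 | −0.08 |
| 10% v 30% | 0.5 | −0.25 | −0.13 |

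Swapping the shares reverses the signs. A simulation of the same model agreed within 0.01 grade and left the overall randomized difference at zero.

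**4. Compared with sampling error.** At assumed one-lip shares of 10%, 20% or 30% of 63 per arm, the one-lip subset has 6, 13 or 19 per arm, and the 95% half-width for a mean difference is about 1.09, 0.69 or 0.56. For the remaining 57, 50 or 44 per arm it is about 0.32, 0.34 or 0.36. Each illustrated bias is smaller than the half-width for its subset.

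**5. On the planned scale.** The SAP uses Hodges-Lehmann limits on whole-number scores. Simulating rounded normal scores (assumed means 1.0 to 1.5, SD 0.85, 45 per arm), a shift of 0.10 in one arm left the estimate at 0 in about 98% to 99% of runs. The lower limit was −1 in about 38% to 45% of runs, against 20% to 26% with no shift, and was never below −1.

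**The case against.** The strongest reply is that little depends on this. The non-inferiority claim rests on the whole per-protocol population. The subset table is called supportive, and neither document attaches a margin or a claim to either subset. That stands, and it limits the point to interpretation.

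Three stronger readings are tempting but are not supported.
- *The unblinded injector alone chooses the lips.* The documents do not say so. The result is to satisfy both injector and subject, touch-up is decided in consultation, the subject is blinded, and one eligibility group states a wish beforehand. Blinding the subject does not remove the difficulty, since a blinded subject can still react to how the device performs.
- *A second lip added at touch-up moves the subject to the both-lips group.* No text says that a touch-up may treat a new lip or that it counts toward membership. The accurate criticism is that the classification is undefined.
- *The bias can be quoted as a fraction of the 0.50 margin.* A shift in one arm biases the contrast only so far as selection differs between arms. A mean shift also does not carry over directly to Hodges-Lehmann limits, for which the SAP uses a criterion of −1.0 (the conflict with −0.50 is a separate matter).

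It is also fair to say that planned outputs already show part of the picture. Table 14.2.1.4 gives N per arm in each subset, Tables 14.3.1.1 and 14.3.1.2 give exposure by lip, and Listing 16.2.6.2.1 shows the lips treated. These would reveal an imbalance in shares, but equal counts do not prove that the same kind of subject was selected, and no output restores randomization.

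**Conclusion.** The structural point holds. The subsets are defined by treatment received after assignment, so the device differences within them lack the protection of randomization, and neither document says so. Bias is possible rather than shown: it requires the lips treated to depend on the device and to be related to the score. Under the assumed shares it runs from zero to about 0.25 grade in the one-lip subset and about 0.13 in the both-lips subset, in either direction. The true size and sign cannot be learned from the documents. A reader might infer that the trial's main conclusion is at risk. It is not, because the overall comparison does not use the subsets. This is a cheap improvement to a supportive analysis.

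**What to change.** - Add one field to the Day 1 CRF, completed before the assignment is revealed, stating which lip(s) the subject and Treating Investigator intend to treat.
- In Protocol 8.2, SAP 5.5.1 and Table 14.2.1.4, define the two subsets by that recorded intent.
- Add a count of intended against actual lips by arm.
- For subjects already treated without a recorded intent, keep the as-injected subsets but label them descriptive and non-randomized, and state how a second lip first treated at touch-up is classified for the analysis.

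Cost: one CRF field and a few sentences, with the sponsor and IRB approval that Protocol 10.5 requires for a revision. Intent cannot be recorded retrospectively, and a few subjects will be analysed under an intent that differs from what was done. Nothing in how subjects are treated changes.
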